## **1.0 Objectives**

### **1.1 Study Objectives**

The goal of our research proposal would be to determine if intra-operative ketamine and magnesium decrease the amount of opiate use in the first 24 hours after laparoscopic bariatric surgery.

### **1.2 Primary Study Endpoints**

1. Total hydromorphone use in 1st 24 hours post-operatively.

### **1.3 Secondary Study Endpoints**

1. Pain Scores using Visual Analogue Scale (VAS) [ Time Frame: 1st 24 hours post-op ]
2. Sedation scores using Ramsey Sedation Scale [ Time Frame: 1st 24 hours post-op ]
3. Nausea Scores using PONV Impact Scale Score [ Time Frame: 1st 24 hours post-op ] – see data collection sheet
4. Intraoperative fentanyl use [ Time Frame: Intraoperative period ]
5. Intraoperative minimum alveolar concentration (MAC) of desflurane
6. Sentec CO2 measurements, average PCO2 will be taken every hour [Time Frame: 1st 24 hours post-op].

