## **2.0 Background**

### **2.1 Scientific Background and Gaps**

Post-operative pain control is a crucial aspect of care for any patient undergoing any operation. Management of post-operative pain improves patient satisfaction and leads to earlier mobilization, decreased length of hospital stay and even decreased hospital costs. Opiates are the predominant drug of choice intra-operatively to help control post-operative pain and, while effective, have a long list of serious side effects that may ultimately delay the patient's recovery. Decreasing the respiratory drive is one of most serious side effects of opiate use when attempting to control post-operative pain. This is especially true in the obese population in which other respiratory disorders are more commonplace. These include obstructive sleep apnea (OSA) and obesity hypoventilation syndrome (OHS). The prevalence of OHS in the general adult population is estimated to be 0.15% to 0.3%. In patients undergoing bariatric surgery the incidence is approximately 8%. Achieving adequate safe analgesia in this patient population can be difficult and requires a multimodal approach.

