#### **7.2.4 Day of Surgery Pre-Operation and Operating Room**

During routine check of preoperative vital signs in the SDU the patient will be fitted with the Sentec CO2 monitor. Standard preoperative checklists/questions will be asked by the nursing staff as per hospital protocol.

The investigational pharmacy will deliver the appropriate study medication to the OR window, or the drug will be picked up by the coordinator at the investigational pharmacy. Prior to induction of anesthesia the patient will receive 1-2 mg of IV midazolam for anxiolysis if needed. Anesthesia will be induced with propofol (1.5-2.5 mg/kg) and fentanyl 1-2 $\mu$ g/kg. Muscle relaxant will be administered to facilitate tracheal intubation and to maintain muscular relaxation. Following securement of the endotracheal tube, the study medication will be administered over 10 minutes via an IV infusion pump. Dexamethasone 4 mg and 1 gm of Tylenol IV will be given after the study medication has been delivered, as per standard of care. Maintenance of anesthesia will be with desflurane and fentanyl dosing at the discretion of the primary team. End tidal CO2 will be maintained between 30-35 mm hg (Apollo SW4.5n, Anesthetic Gas Module, Telford,PA, USA). No long-acting opiate will be used. 4 mg ondansetron will be given during skin closure at the end of surgery. Subjects will then be fully reversed and allowed to emerge from anesthesia and will be extubated per the primary anesthesia team. The above protocol is standard care for a patient undergoing a sleeve gastrectomy. The only non-standard part of this anesthetic is the addition of the study medications.

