#### **7.2.5 Post- op**

As per standard of care, the patient will be taken to the post anesthesia care unit (PACU) and set up with standard ASA monitoring as well as the Sentec CO2 monitor which was applied in the SDU.. A hydromorphone patient controlled analgesia (PCA) pump will be set-up by nursing and given to the patient. Standard dosing of 0.2 mg bolus, every 6 minutes with a maximum 2 mg per hour will be the starting dose as is standard for these patients post-operatively. As per standard of care, 1 gm of Tylenol every 8hrs will also be scheduled to be administered via IV route for 1st 24hrs. If reported pain scores are beyond the patients previously determined acceptable pain score (asked pre-operatively per hospital standard) the PACU resident may give additional doses of IV hydromorphone at his/her discretion. When patient meets discharge criteria they will be sent from the PACU to their room with monitoring of continuous pulse oximetry and ETCO2 until 24 hours post-operation.

During the post-operative period, data will be recorded immediately upon arrival to PACU and every 4 hours thereafter with a maximum recording of 24 hours post-op. For study purposes, a data sheet will be assigned to the patient pre-operatively with pre-operative pain anxiety, and PONV scores recorded. The sheet will then be attached to the patients chart and data recorded by the nursing staff. At the end of the 24 hour period the sheets will be collected by one of the research team members.

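### The Sentec PCO2 endpoint is compared without the preoperative value, which costs precision that a baseline covariate would recover at almost no cost

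*Combined protocol and SAP*

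**What the plan says.** Section 1.3, item 6, defines the endpoint as an average PCO2 from the Sentec monitor that "will be taken every hour [Time Frame: 1 st 24 hours post-op". It names no baseline, change score, peak or threshold.

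Section 7.2.4 places the device before surgery: "During routine check of preoperative vital signs in the SDU the patient will be fitted with the Sentec CO2 monitor". The study medication follows later, once the tube is secured. The preoperative items that section 7.2.5 names for the data sheet do not include PCO2: the sheet is assigned "with pre-operative pain anxiety, and PONV scores recorded".

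Section 2.1 explains why ventilation is of interest: "Decreasing the respiratory drive is one of most serious side effects of opiate use when attempting to control post-operative pain". It names sleep apnea and obesity hypoventilation syndrome (OHS), and says of the latter: "In patients undergoing bariatric surgery the incidence is approximately 8" percent. Section 3.2 excludes neither condition.

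Section 9.2 gives methods for pain scores and hydromorphone use only.

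Two statements in section 7.2.5 sit awkwardly with an hourly Sentec endpoint. Recording is 4-hourly: "data will be recorded immediately upon arrival to PACU and every 4 hours thereafter with a maximum recording of 24 hours post-op" (section 11.4 agrees). After PACU the patient goes to the room "with monitoring of continuous pulse oximetry and ETCO 2 until 24 hours post-operation", and Sentec is not named there.

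**The concern.** This is the only endpoint that measures ventilation directly, and reduced respiratory drive is among the reasons the Background gives for sparing opioids. PCO2 is likely to differ between patients for reasons unrelated to treatment, in particular where chronic hypoventilation is present. A comparison of post-operative values alone leaves all of that variation in the error term. The plan puts the monitor in place at a point where each patient's own starting value could be read, but does not provide for recording it.

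What is at stake is the ability of 36 patients per arm to show or exclude a difference in PCO2. If no difference is found, an adjusted analysis supports a tighter statement than an unadjusted one. The primary endpoint is not touched.

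**Working it through.** **1. The plan's own figure.** Section 9.1 asks for 36 per group, sized on opioid use; there is no sample size for PCO2. Inputs: 48-hour mean 52 mg and SD 22 mg, a 25% reduction to 19.5 mg at 24 hours, one-sided 0.05, 80% power. Halving to 24 hours gives a mean of 26 mg, a difference of 26 − 19.5 = 6.5 mg and an SD of 11 mg. The halved SD is an assumption, since the text gives no 24-hour SD.

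n = 2 × (1.645 + 0.842)² × (11/6.5)² ≈ 35.4, so 36. The figure reproduces, and 36 per arm is used below.

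**2. Detectable PCO2 difference without baseline.** The documents give no SD for PCO2, so results are in SD units, for a comparison of two arms.

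- One-sided 0.05: (1.645 + 0.842) × √(2/36) = 0.59 SD.
- Two-sided 0.05: (1.960 + 0.842) × √(2/36) = 0.66 SD.

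**3. With the preoperative value as covariate.** ANCOVA multiplies the variance by 1 − r², where r is the correlation between the preoperative reading and the patient's post-operative mean. The documents give no r, so a range is shown.

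| Assumed r | ANCOVA variance factor, 1 − r² | Detectable, one-sided | Detectable, two-sided | Effective n per arm, 36/(1 − r²) | Change-score variance factor, 2(1 − r) |
|---|---|---|---|---|---|
| 0.3 | 0.91 | 0.56 SD | 0.63 SD | about 40 | 1.4 |
| 0.5 | 0.75 | 0.51 SD | 0.57 SD | 48 | 1.0 |
| 0.7 | 0.51 | 0.42 SD | 0.47 SD | about 71 | 0.6 |

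The last column shows why the covariate is preferred to subtracting the baseline: a raw change score loses precision when r is below 0.5, and ANCOVA is the more precise of the two at each r shown.

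**4. Imbalance in OHS.** At 8%, 0.08 × 36 = 2.9 such patients are expected per arm. The binomial chance that two given arms differ by three or more is about 27%. If these patients run 10 mmHg higher (an assumption), a difference of three moves the arm means apart by 3 × 10/36 = 0.83 mmHg.

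Set that against the standard error. If OHS were the only source of variation, the SD would be 10 × √(0.08 × 0.92) = 2.7 mmHg and the SE of the difference 2.7 × √(2/36) = 0.64, so 0.83 is 1.3 SE. With a further 5 mmHg SD among all patients (an assumption), the SE is √(5² + 2.7²) × √(2/36) = 1.34, and 0.83 is 0.6 SE. Neither reaches 1.645.

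**5. What an hourly mean does to a short rise.** A rise of R mmHg lasting m minutes adds R × m/60 to that hour's mean. As an illustration with assumed values, 20 mmHg for 10 minutes appears as 20 × 10/60 = 3.3 mmHg. A longer rise stays visible: 10 mmHg for 30 minutes adds 5 mmHg.

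**6. Recording.** Hourly values over 24 hours would be 24 per patient. PACU arrival plus every 4 hours gives at most 1 + 24/4 = 7 recording times. The sections do not say how the hourly averages reach the data sheet.

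**The case against.** The strongest reply is that nothing here is invalid. Randomisation makes the post-operative comparison unbiased, and chance imbalance in patients with high PCO2 is already part of the variance on which the test's error rate rests. That stands. A reader might infer that a few such patients could create a false treatment difference; step 4 shows that the imbalance in question lies well within sampling error. Only the loss of precision remains.

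A reader might also infer that the endpoint conceals the hypoventilation episodes for which the trial was designed, and that a 24-hour peak should replace it. The documents do not support this. Section 1.1 states the goal as opioid use. Section 2.1 speaks of respiratory drive, not of episodes, and an hourly mean is a defensible measure of drive. Several short rises within an hour, or one long one, would still move it. A maximum is prone to artefact and depends on how long the sensor was worn, and no section describes a stored trace from which a peak could be taken.

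Finally, the absence of a baseline is read from silence. The data collection sheet is not among the text available here and may have a space for it. This stands in part: the monitor's early placement is compatible with a baseline reading, but the preoperative items that section 7.2.5 names leave PCO2 out, and no section gives the reading a role in the analysis.

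**Conclusion.** The point holds as one of precision on a secondary endpoint. As written, PCO2 would be compared on post-operative values alone, although a preoperative reading is within easy reach. At 36 per arm, adjustment would lower the detectable difference from 0.59 SD to between 0.56 and 0.42 SD (one-sided 0.05, 80% power). That is worth roughly 4 to 35 additional patients per arm on this endpoint (40 − 36 and 71 − 36).

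The size rests on an assumed correlation of 0.3 to 0.7; at the low end the gain is small. The figures also assume 36 patients per arm with both a preoperative reading and usable post-operative values. They do not depend on the 8% figure or on any mmHg value. The dilution of short rises by minutes/60 is arithmetically sure, but whether such rises occur, and how large they are, is not in the documents; it justifies a supportive summary and no more.

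Separately, the hourly Sentec endpoint, the 4-hourly recording and the ward monitoring that does not name Sentec are not consistent as they stand.

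**What to change.** - **Section 7.2.5, data sheet:** add the preoperative Sentec PCO2, read in the SDU before any sedative or study drug.
- **Sections 1.3 and 9.2:** define the PCO2 outcome as each patient's mean of the hourly values over the first 24 hours, and compare arms by ANCOVA with the preoperative reading as covariate. Do not use a raw change score.
- **Optional, if the monitor stores its trace:** prespecify one supportive summary, such as the peak sustained for a stated minimum duration, fixed before unblinding. It should not become the main PCO2 comparison.
- **Reconcile** the hourly endpoint in section 1.3 with the 4-hourly recording in sections 7.2.5 and 11.4, and with the post-PACU monitoring in section 7.2.5, so that it is clear where the hourly values come from and for how long.

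The cost is one extra recorded number per patient and one degree of freedom in the analysis. It needs no new device, visit or patients. Whether the optional summary is feasible depends on trace storage, which the documents do not describe.

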## **2.0 Background**

### **2.1 Scientific Background and Gaps**

Post-operative pain control is a crucial aspect of care for any patient undergoing any operation. Management of post-operative pain improves patient satisfaction and leads to earlier mobilization, decreased length of hospital stay and even decreased hospital costs. Opiates are the predominant drug of choice intra-operatively to help control post-operative pain and, while effective, have a long list of serious side effects that may ultimately delay the patient's recovery. Decreasing the respiratory drive is one of most serious side effects of opiate use when attempting to control post-operative pain. This is especially true in the obese population in which other respiratory disorders are more commonplace. These include obstructive sleep apnea (OSA) and obesity hypoventilation syndrome (OHS). The prevalence of OHS in the general adult population is estimated to be 0.15% to 0.3%. In patients undergoing bariatric surgery the incidence is approximately 8%. Achieving adequate safe analgesia in this patient population can be difficult and requires a multimodal approach.

### **2.2 Previous Data**

Ketamine and magnesium^8 have each been shown independently to safely improve pain scores and decrease opiate consumption when given intra-operatively. N-methyl-D-aspartate (NMDA) receptor antagonism is the primary mechanism of action by which they are thought to act as analgesics. Both drugs, however, potentially have more than one mechanism by which they achieve analgesia.

## 2.3 Study Rationale

Opioid sparing anesthesia is extremely important in the post-operative obese population. With more and more obese patients entering the operating room a multi-modal approach to analgesia is crucial. Finding effective alternatives to opioid therapy in this population is the rationale of this proposal. Ketamine and magnesium have been well studied and have been proven to be safe adjuncts to a general anesthetic and are used daily by many anesthesia providers for a variety of cases. The purpose of this study is to look at their effects in the obese population specifically, as they may benefit more from opioid sparing therapy relative to normal weight individuals. Currently many anesthesiologists use these drugs in this fashion; however, literature involving ketamine and magnesium in bariatric surgical patients is very sparse.

# 3.0 Inclusion and Exclusion Criteria

## 3.1 Inclusion Criteria

1. Subjects undergoing laparoscopic sleeve gastrectomy
2. Consenting adults age 18-80
3. American Society of Anesthesiologists (ASA) Physical Status classification II to ASA III
4. Required to be hospitalized for at least 24 hours post-op

## 3.2 Exclusion Criteria

1. Patient refusal
2. Chronic opiate use (daily opiate use for >3 months)
3. Chronic Kidney disease (Creatinine>2)
4. History of heart failure
5. Known allergy or adverse effect of ketamine, magnesium or hydromorphone
6. Patients with schizophrenia or bipolar disorder
7. Patient unable to give informed consent
8. Patient with limited or no English fluency

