## 9.0 Statistical Plan

### 9.1 Sample size determination

Up to 250 subjects will be enrolled in order to obtain enough data to determine if a significant difference exists between the treatment groups. This number will allow exclusions and withdrawals, in order to obtain the goal of 36 completed subjects per group.

Based on the Martinez study, the mean (and standard deviation) for the 48-hour morphine use in the ketamine group was 52 mg + 22 mg. Assuming that magnesium would yield a similar result as ketamine, a conservative expectation for the combination of ketamine and magnesium is a 25% reduction for the 24-hour morphine use to 19.5 mg. In order to achieve 80% statistical power with one-sided, 0.05 statistical tests, a sample size of 36 for each of the three groups is needed (total sample size of 108 completed patients for statistical analysis).

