### 9.2 Statistical methods

Our current plan is to use ANOVA, along with pairwise comparisons, to compare the three groups with respect to pain scores (nonparametric ANOVA) and total hydromorphone use (parametric ANOVA) in the first 24 hours post-operatively, to determine whether there are any significant differences. We will use SAS, Version 9.4, for all statistical analyses.

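### The opioid exclusion is set by duration alone, so patients on daily opioids for 3 months or less at surgery may enter a trial whose primary endpoint is opioid consumption (low priority)

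*Combined protocol and SAP*

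**What the plan says.** Section 3.2, item 2, excludes "Chronic opiate use (daily opiate use for >3 months" and sets no limit on current or recent use of shorter duration. Section 1.2 makes total hydromorphone use "in 1 st 24 hours post-operatively" the single primary endpoint. Section 9.2 compares "total hydromorphone use (parametric ANOVA) in the first 24 hours post-operatively" between the three groups, with pairwise comparisons and no baseline covariate.

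No other section that could cover shorter daily use does so:

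- The inclusion criteria (3.1) and removal criteria (3.3.1) do not mention prior opioids.
- Randomisation (7.2.2 and 7.4.3) uses blocks of nine and names no prior-opioid stratum.
- The data sheet described in 7.2.5 is said to carry preoperative pain, anxiety and PONV scores. Prior opioid use is not listed.
- Prior and concomitant therapy (7.4.6.5) is marked not applicable.

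The screening questions (4.3, 4.4) and the data collection sheet (1.3) are separate documents and are not reproduced.

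**The concern.** By excluding long-term daily users, the protocol already treats prior opioid use as relevant to eligibility. Its cut-off looks only at how long use has lasted and not at whether the patient is taking opioids now. Someone with 10 weeks of daily use up to the morning of surgery is admitted, while someone with slightly more than 3 months is not.

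If current daily users need more hydromorphone after surgery for reasons unrelated to study treatment, they form a high-consumption tail on the primary endpoint. An unadjusted comparison of means puts that tail into the error variance. The sample size has no reserve to absorb it, because 36 per group gives almost exactly 80% power under the plan's own assumptions.

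**Working it through.** **Inputs from section 9.1.** For the cited hip-arthroplasty study, "the mean (and standard deviation) for the 48-hour morphine use in the ketamine group was 52 mg + 22 mg". The plan then expects "a 25% reduction for the 24-hour morphine use to 19.5 mg". Halving 52 gives 26 mg for 24 hours, and 26 × 0.75 = 19.5, so the difference is 6.5 mg. The 24-hour SD is not stated. Halving 22 gives 11 mg, which is an inference. The design uses "one-sided, 0.05 statistical tests", 80% power and 36 per group.

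**Reproducing the plan's figure.** n = 2(1.645 + 0.842)² × 11² / 6.5² = 35.4, rounded up to 36 per group. This matches, so 11 mg is very probably the SD used; an SD of 15.56 (22/√2) would need 71 per group and an SD of 22 would need 142. The standard error of a difference is 11 × √(2/36) = 2.59 mg, and exact noncentral-t power at 36 per group is 0.799.

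**Adding short-duration daily users.** Let a share *p* of each arm use *k* times the usual amount. Neither value is in the documents, so both are assumptions. For an arm with mean μ:

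variance = (1−p)·11² + p·s² + p(1−p)·[μ(k−1)]²

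Here s is the SD among these patients, either 11 (unchanged) or 11k (scaled). The variances of the 26 mg and 19.5 mg arms are averaged. The difference is either held at 6.5 mg or scaled to 6.5 × [1 + p(k−1)].

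**Worked case: p = 0.05, k = 2, scaled SD, difference held.**

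- 26 mg arm: 0.95 × 121 + 0.05 × 484 + 0.0475 × 26² = 114.95 + 24.20 + 32.11 = 171.26, SD 13.09.
- 19.5 mg arm: 114.95 + 24.20 + 0.0475 × 19.5² = 157.21, SD 12.54.
- Average variance 164.24, standard error √(2 × 164.24/36) = 3.02 mg, noncentrality 6.5/3.02 = 2.15, power 0.687.

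**Power at 36 per group, one-sided 0.05 (base 0.799).**

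| k | SD in these patients | Difference | 1% | 2% | 5% | 10% |
|---|---|---|---|---|---|---|
| 1.5 | unchanged | scaled | 0.799 | 0.798 | 0.799 | 0.800 |
| 1.5 | unchanged | held | 0.795 | 0.792 | 0.781 | 0.766 |
| 1.5 | scaled | held | 0.791 | 0.783 | 0.760 | 0.726 |
| 2 | unchanged | scaled | 0.791 | 0.784 | 0.767 | 0.748 |
| 2 | unchanged | held | 0.784 | 0.770 | 0.731 | 0.677 |
| 2 | scaled | scaled | 0.781 | 0.765 | 0.723 | 0.675 |
| 2 | scaled | held | 0.774 | 0.750 | 0.687 | 0.604 |

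The figures are in morphine milligrams, as in 9.1. A constant conversion to hydromorphone would leave the power unchanged.

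**Chance imbalance.** At k = 2, one extra such patient in an arm of 36 shifts its mean by 26/36 = 0.7 mg, and two shift it by 1.4 mg. Against a standard error of 2.6 mg that is about 0.3 to 0.6 of a standard error.

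**The case against.** The strongest reply is that this is a choice of threshold and not an error. The protocol names a concept, chronic use, defines it, and contradicts it nowhere. It does not say that the exclusion is meant to remove opioid-tolerant patients, and nothing shows that any sleeve-gastrectomy candidate at this centre takes opioids daily. This stands: the documents support only that such patients may enter, not that they do.

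Second, the planning SD comes from another trial whose eligibility rules are not described here. If that trial admitted short-term opioid users, its SD already contains this variance and the mixture calculation counts it twice. This also stands, and it is why the SD assumption has to be stated beside the result.

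Third, the unseen screening questions and data sheet might ask about any opioid use. That is possible. However, sections 4.2 and 4.4 use the questionnaire to apply the eligibility criteria, so it cannot be taken to close the gap. Equally, one cannot say that prior use goes unrecorded.

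Two stronger readings are tempting. A reader might infer that the criterion biases the treatment comparison. It does not, because randomisation balances these patients on average. A reader might also infer that one or two of them falling unevenly could decide the result. At 0.7 to 1.4 mg the shift is ordinary sampling noise against the 6.5 mg target, and it is the same variance already counted in the power figures, not a second harm.

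**Conclusion.** The gap in eligibility is real on the text: current daily use of 3 months or less is neither excluded nor covered by any stated stratum or covariate, in a trial with an opioid-consumption endpoint. Its effect is a possible loss of precision only.

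The size cannot be fixed from the documents. Within the ranges assumed above, power runs from 0.80, which is no loss, to 0.60. The low end needs a 10% share, doubled use, a doubled SD in these patients and a difference that does not grow with use, so it should not be read as the expected result. At a 1% share power stays at 0.77 or above throughout the table. All of this rests on the inferred SD of 11 mg describing a population without such patients.

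This is a low-priority tightening, worth making because it is cheap. It does not call the sample-size arithmetic into question, which reproduces.

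**What to change.** Extend exclusion 2 in section 3.2 so that it covers both use beyond 3 months and current daily opioid use at the time of screening or surgery, whatever its duration. If a look-back window is wanted, the sponsor should choose and justify it, since the documents offer no basis for a particular length. Add the matching item to the screening questionnaire that every candidate already answers.

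If the sponsor prefers to keep these patients, record preoperative opioid use (yes/no) at baseline and name it in 9.2 as a covariate in the primary hydromorphone analysis.

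The first option costs one line of protocol and one question. A few patients become ineligible, and the result no longer covers recent daily opioid users. Section 9.1 allows up to 250 enrolled for 108 completed, although that margin is also meant for other exclusions and withdrawals. The second option costs one baseline field and one model term. It keeps the wider population, but adjusts only for the average difference between users and non-users and not for a larger spread among users.
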